# LIST OF ABBREVIATIONS

Abbreviations and Special Terms	Definition	
AA	alopecia areata	
AD	atopic dermatitis	
AE	adverse event	
ALT	alanine aminotransferase	
AST	aspartate aminotransferase	
BID	twice daily	
BMI	body mass index	
BSA	body surface area	
CFR	Code of Federal Regulations	
CSR	Clinical Study Report	
CTCAE	Common Terminology Criteria for Adverse Events	
DSMB	Data Safety Monitoring Board	
ECG	electrocardiogram	
eCRF	electronic case report form	
EDC	electronic data capture	
EOS	end of study	
EOT	end of treatment	
F-BSA	facial body surface area	
FAS	full analysis set	
FDA	Food and Drug Administration	
FSH	follicle-stimulating hormone	
F-VASI	Face Vitiligo Area Scoring Index	
F-VASI25/50/75/90	≥ 25%/ 50%/ 75%/ 90% improvement from baseline in Face Vitiligo Area Scoring Index score	
GCP	Good Clinical Practice	
GDPR	General Data Protection Regulation	
HIPAA	Health Insurance Portability and Accountability Act	
HIV	human immunodeficiency virus	
HRT	hormone replacement therapy	
IB	Investigator's Brochure	
ICF	informed consent form	
ICH	International Conference on Harmonisation	
ID	identification	
IEC	independent ethics committee	
IRB	institutional review board	

Abbreviations and	D. Chaidian		
Special Terms IRT	Definition		
	interactive response technology  Janus kinase		
JAK M. IDDA			
MedDRA	Medical Dictionary for Regulatory Activities		
NB-UVB	narrow-band ultraviolet B		
PK	pharmacokinetic		
PUVA	psoralen and ultraviolet A		
QD	once daily		
RSI	reference safety information		
SAE	serious adverse event		
SD	standard deviation		
SoA	schedule of assessments		
SOP			
	standard operating procedure		
SPF	sun protection factor		
SUSAR	suspected unexpected adverse reaction		
T-BSA	total body surface area		
TEAE	treatment-emergent adverse event		
T.D. CVA			
T-PaGVA	total body assessment of Patient's Global Vitiligo Assessment		
TOLL			
TSH	thyroid-stimulating hormone		
T-VASI	total body Vitiligo Area Scoring Index		
T-VASI25/50/75/90	≥ 25%/ 50%/ 75%/ 90% improvement in total body Vitiligo Area Scoring Index		
TYK	tyrosine kinase		
ULN	upper limit of normal		
UV	ultraviolet		
VASI	Vitiligo Area Scoring Index		
WHO	World Health Organization		
WOCBP	women of childbearing potential		

#### 1. PROTOCOL SUMMARY

#### **Protocol Title:**

A Safety and Efficacy Study of Ruxolitinib Cream Combined With Narrow-Band Ultraviolet B Phototherapy in Participants With Vitiligo

Protocol Number: INCB 18424-217

### **Objectives and Endpoints:**

Table 1 presents the primary objective and endpoint.

**Table 1:** Primary Objective and Endpoint

Objective	Endpoint		
Primary			
To evaluate the efficacy of ruxolitinib cream in combination with NB-UVB in participants with vitiligo.	Change from baseline in T-VASI at Week 48.		

### **Overall Design:**

Table 2 presents the key study design elements. Further study details are presented after the table.

**Table 2:** Key Study Design Elements

Study Phase	Phase 2		
Clinical Indication	Patients with nonsegmental vitiligo		
Population Males and female participants, aged $\geq 12$ years, who have vitiligo with $\geq 0.5$ F-VASI, $\geq 3.0$ T-VASI (body areas not including the face), and to body vitiligo area (facial and nonfacial) not exceeding 10% BSA.			
Number of Participants	Approximately 50 participants will receive ruxolitinib 1.5% cream BID		
Study Design	Open-label		
Estimated Duration of Study Participation	Screening: Up to 30 days Treatment period: 48 weeks Safety follow-up: 30 days after last application of study drug or last study visit Total: Up to approximately 56 weeks		
DSMB/DMC	No		
Coordinating Principal Investigator			

#### **Treatment Groups and Duration:**

This is an open-label study in which participants will apply ruxolitinib 1.5% cream BID to all depigmented areas up to 10% BSA for up to 48 weeks. Participants should continue to treat depigmented areas identified for treatment at baseline regardless of whether the area begins to improve or fully repigment.

On Day 1, all participants will apply ruxolitinib 1.5% cream BID as monotherapy. At Week 12, participants will apply ruxolitinib 1.5% cream alone or in combination with NB-UVB based on improvement in T-VASI score. Participants who have < T-VASI25 will have NB-UVB phototherapy added to their ruxolitinib 1.5% cream BID regimen (Group A). NB-UVB will be given 3 times per week through Week 48 (36 weeks). Participants who have ≥ T-VASI25 at Week 12 will continue on ruxolitinib 1.5% cream BID alone (Group B). For participants who receive combination therapy, NB-UVB machines will be supplied by the sponsor for at home use during the study.

Figure 1 presents the study design schema. Table 3 presents the schedule of activities for the monotherapy portion of the study (screening through Week 12). Table 4 presents the schedule of activities for Week 16 through the end of the study.

Figure 1: Study Design Schema

[figure not shown]

 Table 3:
 Schedule of Assessments for Screening Through Week 12

	Screening	Treatment Run-In				
	Days		Week 4	Week 8	Week 12	
Procedure	-30 to −1	Day 1	(± 3 d)	(± 3 d)	(± 3 d)	Notes
Administrative procedures	1 1		1		1	
Informed consent	X					Section 8.1.1
Contact IRT	X	X	X	X	X	Section 8.1.3
Inclusion and exclusion criteria	X	X				Section 5
Demography	X					Section 8.1.5.1
General and vitiligo medical history	X					Section 8.1.5.2
Prior/concomitant medications	X	X	X	X	X	Section 6.6
Apply study cream		X	X	X	X	Should be applied by the participant under direct supervision of the site staff. Study cream should be applied after PK or translational blood draws on applicable days.
Dispense (D) and return (R) study cream and reminder/diary cards		D	R/D	R/D	R/D	All tubes of study drug to be weighed before dispensing and when returned. Tubes may not be redispensed.
Collect study cream tubes and collect/review study cream diary cards			X	X	X	
Assess compliance of study cream			X	X	X	Compliance is based on the number of applications. Section 6.4.
Safety assessments						
AE assessment*	X	X	X	X	X	*If an AE is noted, relevant body systems should be physically examined in a targeted physical exam.  Section 8.3.2  Ad hoc photography of skin-related AEs should occur as applicable. Section 8.2.5
Comprehensive physical examination	X				X	Section 8.3.2
Vital signs	X	X	X	X	X	Section 8.3.3
12-lead ECG	X					12-lead ECG performed within 2 months before baseline is acceptable. Section 8.3.4

Table 3: Schedule of Assessments for Screening Through Week 12 (Continued)

	Screening		Treatmen	ıt Run-In		
	Days		Week 4	Week 8	Week 12	7
Procedure	−30 to −1	Day 1	(± 3 d)	(± 3 d)	(± 3 d)	Notes
Efficacy assessments				1	1	
F-BSA	X	X	X	X	X	Section 8.2.1
T-BSA	X	X	X	X	X	Includes facial and nonfacial areas. Section 8.2.1
F-VASI	X	X	X	X	X	Section 8.2.2
T-VASI	X	X	X	X	X	Includes facial and nonfacial areas. Section 8.2.2
				1		
Photography of face	X	X*			X	*If photo quality at screening is not adequate, the
Photography of nonfacial target area	X	X*			X	photography may be repeated on Day 1. Section 8.2.5
Laboratory assessments	X	X			X	Section 8.3.5
Hematology and chemistry assessments Serology and thyroid testing	X	Λ			Λ	Section 8.3.5 Section 8.3.5.2
Urinalysis  Urinalysis	X					Section 8.3.5.2 Section 8.3.5
	X					Section 6.3.3
FSH						S
Pregnancy testing (serum)	X					Section 8.3.5.1
Pregnancy testing (urine)	1	X	X	X	X	Section 8.3.5.1

Table 3: Schedule of Assessments for Screening Through Week 12 (Continued)

	Screening		Treatmen	t Run-In		
Procedure	Days -30 to -1	Day 1	Week 4 (± 3 d)	Week 8 (± 3 d)	Week 12 (± 3 d)	Notes
PK and translational assessments						
PK blood draw			X		X	Blood samples must not be drawn from the area that has been treated with study cream.  Samples will be drawn at preapplication. Section 8.4
Vitamin D assessment	X	X			X	

Note: Unscheduled visits may occur at any time at the investigator's discretion, and appropriate clinical and laboratory tests may be performed, as clinically indicated.

 Table 4:
 Schedule of Assessments Week 16 Through End of Study

						Safety Follow-Up	Notes
Procedure	Week 16 (± 3 d)	Week 24 (± 7 d)	Week 32 (± 7 d)	Week 40 (± 7 d)	Week 48 (EOT) (± 7 d)	30 days (EOT*+7 d) (EOS)	*After last application of study cream or last visit.
Administrative procedures							
Contact IRT	X	X	X	X	X	X	Section 8.1.3
Prior/concomitant medications	X	X	X	X	X	X	Section 6.6
Apply study cream	X	X	X	X			Should be applied by the participant under direct supervision of the site staff. Study cream should be applied after PK or translational blood draws on applicable days.
Dispense (D) and return (R) study cream and reminder/diary cards	R/D	R/D	R/D	R/D	R		All tubes of study drug to be weighed before dispensing and when returned. Tubes may not be redispensed.
Collect study cream tubes and collect/review study cream diary cards	X	X	X	X	X		
Assess compliance of study cream	X	X	X	X	X		Compliance is based on the number of applications. Section 6.4
Assess compliance with NB-UVB	X	X	X	X	X		Compliance is based on the number of sessions recorded by the NB-UVB machine. Section 6.4
Safety assessments							
AE assessment*	X	X	X	X	X	X	*If an AE is noted, relevant body systems should be physically examined in a targeted physical exam.  Section 8.3.2  Ad hoc photography of skin-related AEs may occur as applicable. Section 8.2.5
Comprehensive physical examination		X			X		Section 8.3.2
Vital signs	X	X	X	X	X	X	Section 8.3.3

Table 4: Schedule of Assessments Week 16 Through End of Study (Continued)

						Safety	
			T	 	TT 1 40	Follow-Up	Notes
	Week 16	Week 24	Week 32	Week 40	Week 48 (EOT)	30 days (EOT*+7 d)	
Procedure	(± 3 d)	(± 7 d)	(± 7 d)	(± 7 d)	(± 7 d)	(EOS)	*After last application of study cream or last visit.
Efficacy assessments				I		T	
F-BSA	X	X	X	X	X	X	Section 8.2.1
T-BSA	X	X	X	X	X	X	Includes facial and nonfacial areas. Section 8.2.1
F-VASI	X	X	X	X	X	X	Section 8.2.2
T-VASI	X	X	X	X	X	X	Includes facial and nonfacial areas. Section 8.2.2
Photography of face		X		X	X		Section 8.2.5
Photography of nonfacial target area		X		X	X		
Laboratory assessments	_						
Hematology and chemistry assessments		X		X	X		Section 8.3.5
Pregnancy testing (serum)						X	Section 8.3.5.1
Pregnancy testing (urine)	X	X	X	X	X		Section 8.3.5.1

Table 4: Schedule of Assessments Week 16 Through End of Study (Continued)

						Safety Follow-Up	Notes
Procedure	Week 16 (± 3 d)	Week 24 (± 7 d)	Week 32 (± 7 d)	Week 40 (± 7 d)	Week 48 (EOT) (± 7 d)	30 days (EOT*+7 d) (EOS)	*After last application of study cream or last visit.
PK and translational assessment	ts						
PK blood draw	X*						Blood samples must not be drawn from an area that has been treated with study cream.  Samples will be drawn at preapplication. Section 8.4  *Only participants starting combination at Week 12.
Vitamin D assessment		X		X	X	X	

Note: Unscheduled visits may occur at any time at the investigator's discretion, and appropriate clinical and laboratory tests may be performed, as clinically indicated.

#### 2. INTRODUCTION

#### 2.1. Ruxolitinib Cream

Ruxolitinib cream is in Phase 3 development for the treatment of vitiligo and is a topical formulation of ruxolitinib phosphate, an inhibitor of the JAK family of protein TYKs. Janus kinases are intracellular signaling enzymes that act downstream of key proinflammatory cytokines implicated in vitiligo pathogenesis. Ruxolitinib is a novel, potent, and selective inhibitor of the JAKs, specifically JAK1 and JAK2 with modest to marked selectivity against TYK2 and JAK3. Ruxolitinib potently (IC $_{50}$  < 5 nM) inhibits JAKs, yet it does not significantly inhibit (< 30% inhibition) a broad panel of 26 kinases when tested at 200 nM (approximately 100 times the average IC $_{50}$  value for JAK enzyme inhibition). Ruxolitinib-mediated inhibition of JAK signaling may be an effective strategy for vitiligo treatment.

### 2.2. Background

Vitiligo is an autoimmune pigmentary disease that is estimated to affect 0.5% to 2% of the population worldwide (Krüger and Schallreuter 2012) and is characterized by depigmented patches of skin with a selective loss of melanocytes. The natural course of the disease is generally unpredictable, but it is often progressive. Some degree of spontaneous repigmentation may occur in 10% to 20% of patients; however, it is typically not cosmetically acceptable (Castanet and Ortonne 1997).

Vitiligo is considered a serious disease owing to its substantial psychological burden on patients and its progressive course if left untreated. Involvement of exposed skin (eg, face and hands) can have a major negative impact on self-esteem and quality of life (Silverberg and Silverberg 2013).

Currently, there is no approved drug treatment for repigmentation in vitiligo. The management of vitiligo is empirical and based on the most recent consensus guidelines (American Academy of Dermatology, Gawkrodger et al 2008, Taieb et al 2013, Vitiligo Research Foundation). In general, first-line treatments consist of topical steroids and calcineurin inhibitors, which may be most useful for treating disease that is localized. However, this use is off-label, there are inconclusive (or insufficient) data supporting their efficacy, many have restrictions on duration of chronic use, and AEs can limit their tolerability. Second-line treatments consist of phototherapy (NB-UVB and PUVA) and systemic steroid treatment. However, phototherapy regimens typically require 2 to 3 treatments per week, and 12 to 24 months of continuous phototherapy may be necessary to acquire maximal repigmentation (Taieb et al 2013); relapses are common. Third-line treatments consist of surgical grafting techniques and depigmenting treatments. Surgery is best indicated for stable and localized forms of vitiligo, and only a small number of patients with vitiligo are considered suitable candidates. All of these treatments can have adverse effects that limit their use.

No available product or therapy is able to modify the course of vitiligo disease and produce a long-lasting effect. Given the lack of approved therapies, safety concerns, and modest effectiveness of current off-label drug treatments, there is a need to identify a safe and effective new treatment for vitiligo.

### 2.3. Clinical Efficacy and Safety Data With Ruxolitinib Cream

The clinical efficacy and safety of ruxolitinib cream in vitiligo has been evaluated in over 800 participants in 3 randomized, vehicle-controlled studies, 1 Phase 2 (157 participants) and 2 Phase 3 studies (674 participants).

Study INCB 18424-211 evaluated 4 regimens of ruxolitinib cream (1.5% BID, 1.5% QD, 0.5% QD, 0.15% QD) versus vehicle BID for 24 weeks in adults. In INCB 18424-211, all participants initially randomized to vehicle BID and participants initially randomized to 0.15% QD who did not achieve  $\geq$  25% improvement from baseline in F-VASI25 were rerandomized to 1 of the 3 higher strength groups for an additional 28 weeks. All other participants maintained in the same treatment until Week 52. After Week 52, participants could receive open-label 1.5% BID for an additional 104 weeks. The primary endpoint was the proportion of participants who achieved a  $\geq$  50% improvement from baseline in F-VASI50 at Week 24.

In Study INCB 18424-211, all ruxolitinib treatment groups demonstrated clinically meaningful efficacy and superiority over vehicle. The proportion of participants who achieved an F-VASI50 at Week 24 was statistically significantly greater for ruxolitinib cream versus vehicle with response rates of 32.3%, 25.8%, 50.0%, and 45.5% for ruxolitinib cream 0.15% QD, 0.5% QD, 1.5% QD, and 1.5% BID, respectively, and 3.1% for vehicle. The proportion of participants who achieved an F-VASI75 at Week 24 was also statistically significantly greater for ruxolitinib cream versus vehicle with response rates of 9.7%, 16.1%, 16.7%, and 30.3% for ruxolitinib cream 0.15% QD, 0.5% QD, 1.5% QD, and 1.5% BID, respectively, and 0% for vehicle.

In Study INCB 18424-211, improvements in T-VASI were observed at both Weeks 24 and 52. The proportion of participants who achieved a T-VASI50 at Week 24 was also statistically significantly greater for ruxolitinib cream 0.15% QD, 0.5% QD, 1.5% QD, and 1.5% BID compared with vehicle with response rates of 16.1%, 6.5%%, 23.3%, and 12.1%, respectively, compared with 0% in vehicle treated participants. Continued improvement in participants treated with 0.5% QD, 1.5% QD, and 1.5% BID through Week 52 was observed with response rates in T-VASI50 of 25.8%, 30.0%, and 36.4%, respectively.

In participants with vitiligo in Study 18424-211, the incidence and severity of TEAEs among participants who applied ruxolitinib cream were generally similar to those in participants who applied vehicle cream during the vehicle-controlled period; 67.2% and 62.5% of participants on active treatment and vehicle, respectively, had at least 1 TEAE; 0.8% and 0% of participants on active treatment and vehicle, respectively, had at least 1 Grade 3 or higher TEAE. The most frequently reported TEAEs in the active treatment groups during the vehicle-controlled period were acne (12.0%), application site pruritus (10.4%), pruritus (8.8%), and viral upper respiratory tract infection (6.4%). The most common events by preferred term occurred at a comparable incidence for participants on vehicle cream with the exception of acne, which was more common in participants on active treatment. With continued exposure for the 3 highest application strength groups, acne (14.9%), pruritus (12.8%), application site pruritus (7.4%), and viral upper respiratory tract infection (10.6%) remained among the most common TEAEs. No serious TEAE had a fatal outcome nor were they considered related to the study cream by the investigator. There were no clinically meaningful changes in chemistry or hematology parameters, and no clinically meaningful changes were noted for vital signs.

In Study INCB 18424-211, after Week 52, a subset of participants were offered optional concomitant NB-UVB phototherapy while continuing open-label treatment with ruxolitinib 1.5% cream BID. Participants could start phototherapy at any time during the open-label period. Nineteen participants received add-on NB-UVB for ≥ 12 weeks (Pandya et al 2021), with 3 times per week being the most common phototherapy regimen. Among these 19 participants, 15 participants (78.9%) had further improvement in F-VASI and 18 participants (94.7%) had further improvement in T-VASI after the addition of NB-UVB to the ruxolitinib cream regimen. Only 4 participants (21%) who received concomitant NB-UVB therapy had AEs, all of which were Grade 1 or 2 in severity and none were related to treatment.

Studies INCB 18424-306 and -307 are identically-designed, randomized, vehicle-controlled, Phase 3 studies in adolescent and adult participants (≥ 12 years old, ~10% of whom were adolescents) with vitiligo. Participants received blinded study treatment for 24 weeks and were then offered the opportunity to receive an additional 28 weeks of treatment with ruxolitinib cream 1.5% BID. NB-UVB therapy was not allowed in the Phase 3 studies.

Both ongoing Phase 3 studies (INCB 18424-306 and -307) studies met the primary endpoint (p < 0.0001 for both studies), demonstrating that significantly more participants treated with ruxolitinib cream 1.5% twice daily (BID) achieved a  $\geq$  75% improvement from baseline in the facial vitiligo area scoring index (F-VASI75) compared to participants treated with a vehicle control at Week 24. Safety and tolerability in the Phase 3 studies were similar to Study INCB 18424-211 in that the rate of Grade 3 TEAEs, SAEs, and TEAEs leading to discontinuation was low. Further, there were no significant TEAEs or application site events and no clinically relevant hematological changes.

### 2.4. Study Rationale

NB-UVB phototherapy is thought to stimulate the proliferation of melanocytes and melanogenesis, thereby acting in coordination with JAK inhibition, which creates a more favorable immune environment for melanocyte survival by inhibiting the autoimmune response. In Study INCB 18424-211, the addition of phototherapy to ruxolitinib cream in participants with vitiligo was well tolerated; the frequency of adverse events was low, and none were related to treatment (Pandya et al 2021). The addition of NB-UVB phototherapy to ruxolitinib cream resulted in further substantial improvement in repigmentation, including in participants who did not achieve F-VASI50 at Week 24. The current study will investigate these findings in a larger study.

This study is a 2-part, open-label study examining the addition of NB-UVB to ruxolitinib 1.5% cream BID. Approximately 50 participants will receive ruxolitinib 1.5% cream BID for 12 weeks. At Week 12, participants will be assigned to ruxolitinib 1.5% cream alone or in combination with NB-UVB (3 times per week through Week 48) based on the improvement in T-VASI (see Figure 1). Participants who have < T-VASI25 will receive the combination of NB-UVB phototherapy and ruxolitinib 1.5% cream BID (Group A). Participants who have ≥ T-VASI25 at Week 12 will continue on ruxolitinib 1.5% cream BID alone (Group B).

In Study INCB 18424-211, 21.2% of participant who applied ruxolitinib 1.5% cream BID achieved a T-VASI25 at Week 12. T-VASI25 at Week 12 represents a reasonable outcome showing that the participant is having a response to ruxolitinib cream and will potentially benefit from ruxolitinib cream alone. In participants that do not achieve a T-VASI25 at Week 12, NB-UVB will be added to possibly increase the response rate.

NB-UVB phototherapy administered 3 times per week has been chosen as the regimen for this study as this regimen has been shown to induce repigmentation (Mohammad et al 2017). This combination regimen should provide adequate stimulation to the melanocytes to augment the repigmentation provided by ruxolitinib cream alone.

The primary purpose of this study is to evaluate mean percentage change from baseline of T-VASI at Week 48. Additionally, a secondary endpoint is the safety and tolerability of combination therapy (ruxolitinib cream plus NB-UVB) in participants with vitiligo.

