### 3. OBJECTIVES AND ENDPOINTS

Table 5 presents the objectives and endpoints.

**Table 5:** Objectives and Endpoints

Objectives	Endpoints
Primary	
To evaluate the efficacy of ruxolitinib cream in combination with NB-UVB in participants with vitiligo.	Change from baseline in T-VASI at Week 48.
Secondary	
To evaluate the safety and tolerability of ruxolitinib cream in combination with NB-UVB.	Occurrence of AEs and evaluation of vital signs and laboratory data.
To further evaluate the efficacy of ruxolitinib cream in combination with NB-UVB in participants with vitiligo.	
 
Proportion of participants achieving F-VASI50/75/90 at each postbaseline visit.
 
Proportion of participants achieving T-VASI50/75/90 at each postbaseline visit.
 
Change and percentage change from baseline in F-VASI/T-VASI at each postbaseline visit.
 
Change and percentage change from baseline in F-BSA/T-BSA at each postbaseline visit.
 

To evaluate the ruxolitinib PK in plasma after treatment with ruxolitinib cream in combination with NB-UVB.	Population-based (trough) plasma concentrations of ruxolitinib at Weeks 4, 12, and 16.

**Table 5:** Objectives and Endpoints (Continued)

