#### 5.1. Inclusion Criteria

Participants are eligible to be included in the study only if all of the following criteria apply:

- 1. Ability to comprehend and willingness to sign a written ICF for the study (or by parent or legally authorized representative).
- 2. Age  $\geq$  12 years at the time of signing the ICF.
- 3. A clinical diagnosis of nonsegmental vitiligo with depigmented area including all of the following:
  - a.  $\geq 0.5$  F-VASI on the face
  - b.  $\geq$  3.0 T-VASI (body areas not including the face)
  - c. Total body vitiligo area (facial and nonfacial) not exceeding 10% BSA.
- 4. Agree to discontinue all agents used to treat vitiligo from screening through the final safety follow-up visit. Over-the-counter preparations deemed acceptable by the investigator and camouflage makeups are permitted.
- 5. Willingness to take appropriate contraceptive measures to avoid pregnancy or fathering a child for the duration of study participation with the exception of the following:
  - a. Female participants of nonchildbearing potential (ie, or surgically sterile with a hysterectomy and/or bilateral oophorectomy OR postmenopausal [≥ 12 months of amenorrhea without an alternative medical cause]).

Note: Permitted methods in preventing pregnancy (see Appendix A) should be communicated to the participants and their understanding confirmed.

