## 10.4.1.1. Analysis of Primary Efficacy Analysis

The primary efficacy endpoint is the change from baseline in T-VASI at Week 48. For the primary endpoint, summary statistics will include sample size, mean, median, standard deviation, minimum, maximum, and the 95% confidence interval.

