7.3.2. Secondary and Efficacy Analysis

7.3.2.1. Continuous Efficacy Endpoints

By-visit summary statistics for the following continuous measurements, including actual measurement, change from baseline, and percentage change from baseline, will be presented:

• F-VASI/T-VASI

Summary statistics, including sample size, mean, median, standard deviation, minimum, maximum, first quartile, third quartile, and 95% CI, will be presented by visit. In addition, line graphs and mean and standard error plots will be provided.

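### Should percentage change in T-VASI replace absolute change as the primary endpoint because Protocol Section 2.4 names it as the primary purpose?

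*Protocol*

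**What the plan says.** The rationale (Protocol Section 2.4) states: "The primary purpose of this study is to evaluate mean percentage change from baseline of T-VASI at Week 48". The endpoint table in Protocol Section 3 gives the primary endpoint as "Change from baseline in T-VASI at Week 48", and Protocol Table 1 and SAP Table 1 agree. Protocol Section 10.4.1.1 repeats it: "The primary efficacy endpoint is the change from baseline in T-VASI at Week 48". SAP Section 7.3.1 does the same and plans only summary statistics with a 95% confidence interval.

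The unqualified word change means absolute change here, because the same table lists both scales separately among the secondary endpoints: "Change and percentage change from baseline in F-VASI/T-VASI at each postbaseline visit". SAP Section 7.3.2.1 carries this through. For T-VASI, by-visit summaries "including actual measurement, change from baseline, and percentage change from baseline, will be presented", each with a mean, standard deviation and 95% confidence interval. SAP Appendix A plans figures of mean change and of mean percentage change in T-VASI (Figures 4.2.7 and 4.2.8).

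Protocol Section 10.1 says the sample size is not based on power. Protocol Section 10.3 says no formal tests will be done, and SAP Section 3.2 says there is no alpha control.

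**The concern.** Two primary measures are named, and they are not interchangeable. T-VASI is area multiplied by residual depigmentation, so a given proportional repigmentation yields more points in a participant who starts with more disease. The rest of the trial is largely proportional. The Week 12 allocation uses T-VASI25, the responder endpoints are T-VASI50/75/90, and the earlier vitiligo results quoted in Protocol Section 2.3 are responder rates. An unadjusted absolute mean therefore looks out of place.

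If the concern held, the headline estimate would depend on which sentence was followed. It would mix effect with baseline extent, be awkward to set beside other studies, and perhaps carry a wider confidence interval relative to its mean. In an open-label study with no test, two candidate primaries could also let the more favourable one be presented as prespecified.

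**Working it through.** **Inputs from Protocol Section 5.1.** The criteria require at least 0.5 "F-VASI on the face" and at least "3.0 T-VASI (body areas not including the face"), with "Total body vitiligo area (facial and nonfacial) not exceeding 10% BSA". The minimum baseline total is 0.5 + 3.0 = 3.5. The maximum is 10 (10% BSA at 100% depigmentation). The documents give no baseline distribution, no standard deviation and no relation between response and baseline, so all of these are assumed below. The plan contains no sample-size or precision figure to reproduce.

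**1. How far the scales can diverge.** A 50% improvement is 0.5 × 3.5 = 1.75 points at the floor and 0.5 × 10 = 5.0 points at the ceiling. A 20% improvement at baseline 10 (2.0 points) exceeds a 50% improvement at 3.5 (1.75 points).

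**2. How uneven the weighting is.** Mean absolute change = (1/n) Σ bᵢpᵢ, where b is baseline T-VASI and p is fractional change. Each participant's p is therefore weighted by b. The largest ratio between two participants is 10/3.5 = 2.86. The share of total weight held by the half with larger baselines (50% would be equal) is:

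| Assumed baseline distribution on 3.5–10 | Share |
|---|---|
| Left-skewed, scaled beta(4, 1.5) | 56% |
| Right-skewed, scaled beta(1.5, 4) | 59% |
| Uniform: 8.375/(2 × 6.75) | 62% |
| Half at 3.5, half at 10: 10/13.5 | 74% |

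The last row is an artificial extreme.

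**3. What the weighting does to the estimate.** The baseline-weighted percentage equals mean(p) + cov(b, p)/mean(b). Take uniform baselines, a mean improvement of 40%, and p running linearly from 20 points below that mean at one end of the baseline range to 20 points above it at the other. The variance of b is 6.5²/12 = 3.52, so the covariance is (0.20/3.25) × 3.52 = 0.217. The shift is 0.217/6.75 = 0.032. The weighted figure is then about 37% or 43%, against an unweighted 40%.

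**4. Relative precision.** If p is independent of b, then CV²(absolute) = (1 + CV²(p))(1 + CV²(b)) − 1. For uniform baselines, CV²(b) = 3.52/6.75² = 0.0773.

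- Mean 40%, SD 25%: CV(p) = 0.625, and √(1.3906 × 1.0773 − 1) = 0.706. The relative interval is 0.706/0.625 = 1.13 times as wide on the absolute scale.
- Mean 50%, SD 20%: CV(p) = 0.40, and √(1.16 × 1.0773 − 1) = 0.50. The ratio is 1.25.
- Right-skewed baselines, mean 30%, SD 35%: the ratio is 1.04.
- Left-skewed baselines, mean 30–50%, SD 20–35%: ratios are 1.02 to 1.07.

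Independence is itself an assumption. Suppose percentage improvement is negatively correlated with baseline. By simulation, the uniform case with mean 40% and SD 25% falls from 1.13 to 1.03 at correlation −0.4 and to 0.96 at −0.6. The right-skewed case with the same mean and SD falls from 1.08 to 0.99 at −0.5. Not every case falls: uniform baselines with mean 30% and SD 35% rise from 1.07 to 1.14 at −0.6. The sign of any precision difference is therefore not known from the documents.

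**5. What is lost if the rationale sentence is ignored.** Nothing. Mean percentage change in T-VASI at Week 48, the quantity in Section 2.4, is a secondary endpoint with its own 95% confidence interval.

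**The case for a change.** The strongest case for a change is that, in a descriptive open-label study, the primary label is the main protection against choosing a headline after seeing the data. The protocol names two candidates, and SAP Section 11.1 records no reconciliation. Percentage change also fits the T-VASI25 allocation rule and the responder endpoints, and aligning the text looks like a matter of wording.

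Part of this stands. The inconsistency is real and was not noticed. But the sections that define the endpoint and its analysis all agree, and the SAP, which governs the analysis, never treats percentage change as primary. A reader checking the report would find one clear primary endpoint.

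Making percentage change primary is also more than wording. It would replace the primary endpoint, and Protocol Section 11.1 requires Health Authority and IRB/IEC approval before an amendment is implemented. Nor is it clearly better, because percentage change gives more influence to measurement error at low baselines.

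Adjusting the absolute mean for baseline adds little. Within one group, a least-squares adjustment evaluated at that group's own mean baseline returns the raw mean. Between groups no test is planned, and Groups A and B are formed by Week 12 response, so neither adjustment nor a percentage scale would make them comparable. Baseline T-VASI is reported (SAP Section 6.1.2), so a reader can judge the extent of disease. For comparison with the responder rates quoted in Protocol Section 2.3, T-VASI50 is already an endpoint.

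**Conclusion.** No change follows. The sentence in Protocol Section 2.4 is a clerical slip in background text. Correcting it would be tidy but would alter no estimate, interval or table. Choosing between absolute and percentage change is a fair trade-off on which statisticians differ, and the plan reports both at Week 48.

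The baseline weighting is moderate: at most 2.86 to 1 between participants, and about 56% to 62% of the weight on the larger-baseline half under the assumed unimodal or uniform distributions. The relative width of the interval on the absolute scale ranged from 1.02 to 1.25 times that on the percentage scale under independence, and can drop below 1 if response falls as baseline rises. These figures rest on assumed baseline and response distributions. The conclusion does not depend on them, because no test, error rate or sample size turns on the label.
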